3.1.5 Age ≥ 18 years. Because no dosing or adverse event data are currently available on the use of INCB039110 in combination with dabrafenib and trametinib in patients < 18 years of age, children are excluded from this study, but will be eligible for future pediatric trials.

3.1.6 ECOG performance status ≤ 1 (Karnofsky $\geq 70\%$, see Appendix A).

3.1.7 Life expectancy of greater than 3 months in the opinion of the investigator.

3.1.8 Patients must have acceptable organ and marrow function as defined below:

– Leukocytes (WBCs)	$\geq 3,000/\mu\text{L}$
– absolute neutrophil count	$\geq 1,500/\mu\text{L}$
– hemoglobin	$\geq 9 \text{ g/dL}$ (patients may be transfused to this level)
– platelets	$\geq 100,000/\mu\text{L}$
– total bilirubin	$< 1.5 \times$ institutional upper limit of normal

OR

- AST(SGOT)/ALT(SGPT)	> 1.5 x institutional upper limit of normal allowed if direct bilirubin is within normal range.
- PT/INR and PTT	$\leq 2.5 \times$ institutional upper limit of normal
- Serum creatinine	$< 1.3 \times$ ULN ¹ $\leq 1.5 \text{ mg/dL}$ OR creatinine clearance $\geq 50 \text{ mL/min/1.73 m}^2$
- Potassium	$> 3 \text{ and } < 5.5 \text{ mmol/L}$
- Magnesium	$> 1.2 \text{ and } < 2.5 \text{ mg/dL}$

¹Therapeutic levels of anti-coagulation are permitted if clinically indicated, as per section 3.2.15. Thus PT/INR may be >1.3 if therapeutically anti-coagulated.

3.1.9 The effects of INCB039110, dabrafenib, and trametinib on the developing human fetus are unknown. For this reason, women of child-bearing potential must have a *negative serum pregnancy test within 14 days prior to registration and agree to use effective contraception* (barrier method of birth control, or abstinence; hormonal contraception is not allowed due to drug-drug interactions which can render hormonal contraceptives ineffective) *from 14 days prior to registration*, throughout the treatment period, and for 4 months after the last dose of study treatment. Should a woman become pregnant or suspect she is pregnant while she is participating in this study, she should inform her treating physician immediately.

Based on studies in animals, it is also known that dabrafenib may cause damage to the tissue that makes sperm. This may cause sperm to be abnormal in shape and size and could lead to infertility, which may be irreversible.

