5.1 Pre-Treatment Criteria

5.1.1 Screening Visit: Patients must meet criteria at screening as outlined in Section 3.1.

- Of note, screening eligibility labs do not need to be repeated on cycle 1 day 1. If labs are drawn on Cycle 1, Day 1 will not be used to reconfirm eligibility. Eligibility is confirmed at screening; it is not required to be reassessed on Cycle 1, Day 1. Please see section 5.1.2 and the study calendar (Section 10) for information on laboratory studies and treatment parameters.

5.1.2 Hematologic Parameters for treatment:

Absolute Neutrophil Count

- Cycle 1, Day 1: $\geq 1,500/\mu\text{L}$
- Cycle 2 and Beyond, Day 1: Per Table in Section 6.2.1.1

White Blood Cell Count

- Cycle 1, Day 1: $\geq 3,000/\mu\text{L}$
- Cycle 2 and Beyond, Day 1: Per Table in Section 6.2.1.1

Hemoglobin

- Cycle 1, Day 1: $\geq 9\text{ g d/gl}$ (patients may be transfused to this level)
- Cycle 2 and Beyond, Day 1: Per Table in Section 6.2.1.1

Platelets

- Cycle 1, Day 1: $\geq 100,000/\mu\text{L}$
- Cycle 2 and Beyond, Day 1: Per Table in Section 6.2.1.1

5.1.3 Liver Function Parameters for treatment:

Transaminases (AST/ALT):

- Cycle 1, Day 1: $\leq 2.5 \times$ institutional upper limit of normal
- Cycle 2 and Beyond, Day 1: Per Table in Section 6.1.16

Bilirubin

- Cycle 1, Day 1: $< 1.5 \times$ institutional upper limit of normal
OR
 $> 1.5 \times$ institutional upper limit of normal allowed if direct bilirubin is within normal range
- Cycle 2 and Beyond, Day 1: Per Table in Section 6.1.16

5.1.4 Renal Function Parameters for treatment:

Creatinine:

- Cycle 1, Day 1: $\leq 1.5 \text{ mg/mL}$ OR creatinine clearance $\geq 50 \text{ mL/min}/1.73 \text{ m}^2$
- Cycle 2 and Beyond, Day 1: Per Table in Section 6.1.9

5.1.5 All Cycles, Day 1: Patients must have all the following:

- Adequate blood pressure control as detailed in Section 6.1.11.
- ECOG performance status of 0 or 1.
- No evidence of life-threatening medical problems.

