
Criteria for discontinuing study drug: When any of the liver stopping criteria below is met, discontinue trametinib and dabrafenib
 
 1. ALT \geq3xULN and Total bilirubin \geq2x ULN or $>35\%$ direct bilirubin^{1,2} 2. ALT \geq 3xULN and INR >1.5, if INR measured and if subject is not on anticoagulation² 3. ALT \geq5x ULN 4. ALT \geq3x ULN persists for ≥ 4 weeks 5. ALT \geq3x ULN and cannot be monitored weekly for 4 weeks 6. ALT \geq3x ULN associated with symptoms³ (new or worsening) believed to be related to liver injury or hypersensitivity 	
 • Immediately discontinue study treatment. • Do not restart/rechallenge • Perform liver event ASSESSMENT AND WORKUP (see below). • Monitor the subject until liver chemistries resolve, stabilize, or return to baseline (see MONITORING below). If applicable, provide details on required follow up assessments (e.g., follow up for overall survival or disease recurrence or progression). 
MONITORING: In patients stopping for criteria 1-2 (with abnormal TB and INR, indicating potentially more significant liver toxicities):
 
 • Repeat ALT, AST, ALK, and total bilirubin) and perform liver assessment and workup within 24 hours. • Monitor subjects twice weekly until LFT return to normal/baseline or stabilize. • A specialist or hepatology consultation is recommended. 
In patients stopping for criteria 2-6:
 
 • Repeat LFT and perform liver event follow up assessments within 24-72 hours • Monitor subjects weekly until LFTs return to normal/baseline or stabilize. 
ASSESSMENT and WORKUP:
 
 • Viral hepatitis serology.⁴ • If possible, obtain blood sample for PK analysis.⁵ • Serum CPK and LDH. • Fractionate bilirubin, if total bilirubin \geq2x ULN.

Event	Treatment modifications and assessment/monitoring

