	
 • CBC with differential to assess eosinophilia. • Record clinical symptoms of liver injury, or hypersensitivity on AE CRF. • Record concomitant medications (including acetaminophen, herbal remedies, other over the counter medications). • Record alcohol use. 
Additional work up for patient stopping for criteria 1-2 (with abnormal TB and INR, indicating potentially more significant liver toxicities):
 
 • Anti-nuclear antibody, anti-smooth muscle antibody, Type 1 anti-liver kidney microsomal antibodies, and quantitative total immunoglobulin G (IgG or gamma globulins). • Serum acetaminophen adduct HPLC assay (in subjects with likely acetaminophen use in the preceding). • If there is underlying chronic hepatitis B (e.g. positive hepatitis B surface antigen): quantitative hepatitis B DNA and hepatitis delta antibody.⁶ • Liver imaging (ultrasound, MRI, CT) and /or liver biopsy.

Footnotes

1. Serum bilirubin fractionation should be performed if testing is available. If serum bilirubin fractionation testing is unavailable, record presence of detectable urinary bilirubin on dipstick, which indicates direct bilirubin elevations and suggesting liver injury.
2. All events of ALT $\geq 3 \times$ ULN and bilirubin $\geq 2 \times$ ULN ($>35\%$ direct bilirubin) or ALT $3 \times$ ULN and INR >1.5 (if INR measured) may indicate severe liver injury (possible “Hy’s Law”). INR measurement is not required, and the threshold value stated will not apply to subjects receiving anticoagulants.
3. New or worsening symptoms believed to be related to liver injury (such as fatigue, nausea, vomiting, right upper quadrant pain or tenderness, or jaundice) or believed to be related to hypersensitivity (such as fever, rash or eosinophilia)
4. Includes: Hepatitis A IgM antibody; Hepatitis B surface antigen and Hepatitis B Core Antibody (IgM); Hepatitis C RNA; Cytomegalovirus IgM antibody; Epstein-Barr viral capsid antigen IgM antibody (or if unavailable, obtain heterophile antibody or monospot testing); Hepatitis E IgM antibody

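### Liver stopping criterion 1 (Table 6-14) is internally inconsistent: once ALT is at least 3x ULN, a direct bilirubin fraction above 35% forces a permanent stop at any total bilirubin, even a normal one

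*Combined protocol and SAP*

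**What the plan says.** Table 6-14 has two rows.

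- **May continue.** ALT 3 to <5x ULN with total bilirubin <2x ULN, no related symptoms, and weekly monitoring possible for 4 weeks. This row sets no condition on direct bilirubin, but it gives way if any stopping criterion is met.
- **Must stop.** Any one of six criteria ends dabrafenib and trametinib, with no restart or rechallenge. Criterion 1 is ALT ≥3x ULN and "Total bilirubin \geq2x ULN or $>35\%$ direct bilirubin", written without brackets.

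Other text on direct bilirubin:

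- Footnote 2, attached to criterion 1, describes possible Hy's Law cases as ALT ≥3x ULN with "bilirubin $\geq 2 \times$ ULN ($>35\%$ direct bilirubin" in brackets.
- The work-up list says "Fractionate bilirubin, if total bilirubin" is at least 2x ULN.
- The monitoring and additional work-up headings both describe patients stopped under criteria 1-2 as having abnormal total bilirubin and INR.
- Footnote 1 has no threshold: "Serum bilirubin fractionation should be performed if testing is available". Where it is not, a positive urine dipstick is recorded, "which indicates direct bilirubin elevations and suggesting liver injury".
- Eligibility (Section 3.1.8) and the Cycle 1 Day 1 rule (Section 5.1.3) consult direct bilirubin only when total exceeds 1.5x ULN, and compare it with its own normal range: "allowed if direct bilirubin is within normal range".

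From Cycle 2 onward, Section 5.1.3 makes Table 6-14 the Day 1 liver rule.

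**The concern.** The direct-fraction limb of criterion 1 is an alternative to raised total bilirubin, and nothing limits how low the total may be. A ratio can pass 35% because its denominator is small. A patient whose only abnormality is ALT of 3 to <5x ULN can therefore fit the may-continue row and criterion 1 at once, and criterion 1 prevails.

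The two instructions differ greatly. One continues both drugs with weekly laboratory tests. The other withdraws them irreversibly. Section 2.4 itself describes accelerated progression after BRAF inhibitor discontinuation in patients with resistant disease, so an unneeded permanent stop is not a cautious default. After a stop under criteria 1-2 the instruction is "Repeat ALT, AST, ALK, and total bilirubin) and perform liver assessment and workup within 24 hours". That list repeats total bilirubin only, and the work-up fractionates only at total ≥2x ULN, so neither list re-measures the value behind a direct-only stop.

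**Working it through.** The plan gives no figure to reproduce. The check is one of logic, plus an arithmetic bound.

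**1. Reading of criterion 1.** I take the milder literal reading: ALT ≥3x ULN AND (total ≥2x ULN OR direct fraction >35%).

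**2. Where the second limb matters.** ALT ≥5x ULN already stops under criterion 3. Raised INR, persistence for ≥4 weeks, no possibility of weekly monitoring, and symptoms already stop under criteria 2, 4, 5 and 6. What remains is ALT 3 to <5x ULN with none of these. Four states cover that group:

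| Total bilirubin | Direct fraction | Current text | Direct limb deleted | 'or' changed to 'and' |
|---|---|---|---|---|
| <2x ULN | ≤35% | continue | continue | continue |
| <2x ULN | >35% | **stop** | continue | continue |
| ≥2x ULN | ≤35% | stop | stop | **no instruction** |
| ≥2x ULN | >35% | stop | stop | stop |

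The second state is the conflict. At ALT 3.5x ULN, total 0.5x ULN and direct 40%, the may-continue row applies and criterion 1 overrides it. Deleting the limb changes that state alone. With 'and', the third state falls outside both rows.

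**3. Can both bilirubin values be normal?** The documents give no reference ranges, so these are assumptions: direct ULN 0.2, 0.3 or 0.4 mg/dL; total ULN 1.0 or 1.2 mg/dL. Normal direct bilirubin can exceed 35% of the total whenever total < direct ULN / 0.35.

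| Direct ULN (mg/dL) | Total must be below (mg/dL) | As multiple of total ULN 1.0 | As multiple of total ULN 1.2 |
|---|---|---|---|
| 0.2 | 0.2/0.35 = 0.57 | 0.57 | 0.48 |
| 0.3 | 0.3/0.35 = 0.86 | 0.86 | 0.71 |
| 0.4 | 0.4/0.35 = 1.14 | 1.14 | 0.95 |

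So the direct limb can be met at normal totals in every case. The other limb requires 2x ULN.

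**4. Sensitivity to one reporting step.** At an assumed total of 0.3 to 0.5 mg/dL, direct 0.1 mg/dL gives 0.1/0.5 = 20% to 0.1/0.3 = 33% (continue). Direct 0.2 mg/dL gives 0.2/0.5 = 40% to 0.2/0.3 = 67% (permanent stop). An assumed 0.1 mg/dL step decides the outcome.

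**The case against.** The best defence is that the table, read as a whole, shows what was meant. Footnote 2 and the description of criteria 1-2 patients both presuppose abnormal total bilirubin, so a careful investigator would not stop a patient with a normal one. That makes this a drafting inconsistency, and I accept that description. It does not cure the text, because the operative line says otherwise and overrides the may-continue row.

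The trigger is also seldom measured. Study Calendar footnote g lists total bilirubin only, and the work-up fractionates at ≥2x ULN. Below that level, footnote 1 is the only route in Table 6-14 to a direct fraction. This stands and limits the severity.

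A third argument is that direct bilirubin is a real liver signal and the triple combination is untested, so the limb should be given a floor instead of being deleted. A floor below 2x ULN would still contradict the first row and footnote 2. A floor at 2x ULN would make the limb redundant.

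A reader might infer more than the documents support:

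- *That ALT need not be raised.* Strict and-before-or grammar allows it, but footnote 2 ties the rule to ALT ≥3x ULN.
- *That patients with normal bilirubin will be sent for biopsy.* The additional work-up is headed for patients with abnormal total bilirubin and INR, and its last item offers imaging and/or biopsy.
- *That sites will treat identical patients differently.* Sections 3.1.8 and 5.1.3 presume that direct bilirubin can be obtained, and no participating site is shown to lack it.
- *That DLT counts or the MTD are distorted.* A Cycle 1 stop could reach the missed-dose bullet in Section 5.3 only through a chain of conditions, and the documents give no frequency for it.

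**Conclusion.** The point holds as a minor internal inconsistency. In patients with ALT 3 to <5x ULN and no other stopping reason, criterion 1 requires an irreversible stop when the direct fraction exceeds 35% at total bilirubin <2x ULN. Footnote 2, the work-up threshold, the description of criteria 1-2 patients and the first row all imply that this group should not be stopped on that ground.

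The logical result needs no assumed figure; it rests on requiring ALT ≥3x ULN and reading 'or' as written. The figures in mg/dL rest on assumed reference limits, bilirubin values and reporting step, and only illustrate that a ratio has no floor. Frequency is unknown and probably low. No effect on DLT, the MTD or consistency between sites is claimed.

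**What to change.** Restate criterion 1 as: ALT ≥3x ULN and total bilirubin ≥2x ULN. Keep the 35% direct fraction only in footnote 2, where it classifies possible Hy's Law cases. Do not convert 'or' to 'and', for the reason shown in the third state of the table. Leave footnote 1 as it is: fractionation remains useful information for the investigator, and restricting it would discard a safety signal.

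The cost is one line in an amendment and one clinical trade-off. A patient with ALT 3 to <5x ULN, total bilirubin just below 2x ULN and a high direct fraction moves from a mandatory permanent stop to weekly monitoring, with criteria 2-6 still in force. Every stop at ALT ≥3x ULN with total bilirubin ≥2x ULN is kept, including mainly indirect elevations.

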6.1.17 Dabrafenib or Dabrafenib-Trametinib Dose Modification for Venous Thromembolism (VTE)

	Dabrafenib	Trametinib (When Used in Combination)
Uncomplicated DVT or PE	Do not modify the dose.	Withhold trametinib for up to 3 weeks. • If improved to Grade 0-1, resume at a

		lower dose level. • If not improved, permanently discontinue.
Life Threatening PE	Permanently discontinue dabrafenib	Permanently discontinue trametinib.

6.2 INCB039110 Dose modifications

INCB039110 dosing may be reduced in the setting of toxicity. The below table denotes the possible dose levels based on the dose escalation schema.

Current Dose	If Dose Reduction Required	Reduce To
400 mg	→	300 mg
300 mg	→	200 mg
200 mg	→	100 mg
100 mg	→	discontinue

In the event that dabrafenib, trametinib, or both agents need to be discontinued due to toxicity reasons, treatment with INCB039110 may continue at the discretion of the investigator until time of disease progression.

6.2.1 Management of INCB039110 toxicity

The only consistently observed effects of INCB039110 in healthy volunteers, patients with inflammatory diseases and cancer are decreases in neutrophils, hemoglobin and platelet count. For occurrences of grade 3 or 4 events by CTCAE in any of these three categories, the dose reduction table below will be followed. Patients may receive transfusions or growth factor support as indicated in cases of severe toxicity. Dabrafenib and trametinib rarely cause severe effects on blood counts. Therefore, in INCB039110 will be modified in the case of severe decreases in blood counts, assuming that these events are considered treatment related.

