2.2.4 INCB039110 Safety Profile

Summary of Treatment-Emergent Adverse Events Occurring in ≥ 5 Subjects in Study INCB 39110-230 by MedDRA Preferred Term in Decreasing Order of Frequency (Safety Population)

MedDRA Preferred Term	100 mg BID (n = 10)	200 mg BID (n = 45)	600 mg QD (n = 32)	Total (N = 87)
Anemia	3 (30.0)	20 (44.4)	11 (34.4)	34 (39.1)
Fatigue	3 (30.0)	20 (44.4)	8 (25.0)	31 (35.6)
Thrombocytopenia	3 (30.0)	11 (24.4)	8 (25.0)	22 (25.3)
Upper respiratory tract infection	4 (40.0)	10 (22.2)	7 (21.9)	21 (24.1)
Nausea	3 (30.0)	10 (22.2)	6 (18.8)	19 (21.8)
Diarrhea	2 (20.0)	9 (20.0)	6 (18.8)	17 (19.5)
Cough	1 (10.0)	10 (22.2)	5 (15.6)	16 (18.4)
Constipation	1 (10.0)	10 (22.2)	4 (12.5)	15 (17.2)
Edema peripheral	1 (10.0)	10 (22.2)	4 (12.5)	15 (17.2)
Dyspnea	1 (10.0)	6 (13.3)	7 (21.9)	14 (16.1)
Pyrexia	1 (10.0)	7 (15.6)	6 (18.8)	14 (16.1)
Dizziness	0	7 (15.6)	6 (18.8)	13 (14.9)
Pain in extremity	2 (20.0)	8 (17.8)	3 (9.4)	13 (14.9)
Night sweats	1 (10.0)	7 (15.6)	4 (12.5)	12 (13.8)
Abdominal pain	2 (20.0)	5 (11.1)	4 (12.5)	11 (12.6)
Arthralgia	0	8 (17.8)	2 (6.3)	10 (11.5)
Contusion	1 (10.0)	5 (11.1)	4 (12.5)	10 (11.5)
Headache	0	3 (6.7)	6 (18.8)	9 (10.3)
Pruritus	1 (10.0)	6 (13.3)	2 (6.3)	9 (10.3)
Vomiting	0	8 (17.8)	1 (3.1)	9 (10.3)
Hypertension	2 (20.0)	4 (8.9)	2 (6.3)	8 (9.2)
Rash	0	5 (11.1)	3 (9.4)	8 (9.2)
Urinary tract infection	1 (10.0)	3 (6.7)	4 (12.5)	8 (9.2)
Chills	1 (10.0)	4 (8.9)	2 (6.3)	7 (8.0)
Decreased appetite	0	6 (13.3)	1 (3.1)	7 (8.0)
Epistaxis	1 (10.0)	5 (11.1)	1 (3.1)	7 (8.0)

Summary of Treatment-Emergent Adverse Events Occurring in ≥ 5 Subjects in Study INCB 39110-230 by MedDRA Preferred Term in Decreasing Order of Frequency (Safety Population) (Continued)

MedDRA Preferred Term	100 mg BID (n = 10)	200 mg BID (n = 45)	600 mg QD (n = 32)	Total (N = 87)
Pneumonia	1 (10.0)	5 (11.1)	1 (3.1)	7 (8.0)
Aspartate aminotransferase increased	1 (10.0)	4 (8.9)	1 (3.1)	6 (6.9)
Asthenia	1 (10.0)	2 (4.4)	3 (9.4)	6 (6.9)
Blood creatinine increased	2 (20.0)	3 (6.7)	1 (3.1)	6 (6.9)
Bone pain	0	1 (2.2)	5 (15.6)	6 (6.9)
Confusional state	0	2 (4.4)	4 (12.5)	6 (6.9)
Dyspnea exertional	2 (20.0)	2 (4.4)	2 (6.3)	6 (6.9)
Musculoskeletal pain	0	4 (8.9)	2 (6.3)	6 (6.9)
Oropharyngeal pain	0	4 (8.9)	2 (6.3)	6 (6.9)
Stomatitis	0	4 (8.9)	2 (6.3)	6 (6.9)
Acne	0	3 (6.7)	2 (6.3)	5 (5.7)
Alanine aminotransferase increased	2 (20.0)	2 (4.4)	1 (3.1)	5 (5.7)
Back pain	1 (10.0)	4 (8.9)	0	5 (5.7)
Blood bilirubin increased	0	4 (8.9)	1 (3.1)	5 (5.7)

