Common Adverse Events of Dabrafenib-Trametinib Combination vs. Dabrafenib Monotherapy.

The phase 2 portion of study BRF113220 (referred to as Part C) included 3 arms: dabrafenib 150 mg BID + trametinib 2 mg QD, dabrafenib 150 mg BID + trametinib 1 mg QD, and single-agent dabrafenib 150 mg BID. The most common AE resulting in permanent discontinuation was pyrexia (4%). AEs led to dose reductions in 49% and dose interruptions in 67% of patients treated with dabrafenib in combination with trametinib. The table below presents selected adverse reactions and treatment-emergent laboratory abnormalities in this study.

Selected AEs and Laboratory Abnormalities Occurring in $\geq 10\%$ at (All Grades) or $\geq 5\%$ (Grades 3 or 4) of Patients Treated With Dabrafenib in Combination With Trametinib

Adverse Reaction or Laboratory Abnormality	Dabrafenib + Trametinib 2mg (n=55)		Dabrafenib + Trametinib 1mg (n=54)		Dabrafenib (n=53)	
	All Grades ^a	Grades 3 and 4	All Grades ^a	Grades 3 and 4	All Grades ^a	Grades 3 and 4
General disorders and administrative site conditions						
Pyrexia	71	5	69	9	26	0
Chills	58	2	50	2	17	0
Fatigue	53	4	57	2	40	6
Edema peripheral ^b	31	0	28	0	17	0
Skin and subcutaneous tissue disorders						
Rash ^c	45	0	43	2	53	0
Night sweats	24	0	15	0	6	0
Dry skin	18	0	9	0	6	0
Dermatitis acneiform	16	0	11	0	4	0
Actinic keratosis	15	0	7	0	9	0
Erythema	15	0	6	0	2	0
Pruritis	11	0	11	0	13	0
Gastrointestinal disorders						
Nausea	44	2	46	6	21	0
Vomiting	40	2	43	4	15	0
Diarrhea	36	2	26	0	28	0
Metabolism and nutritional disorders						
Decreased appetite	22	0	30	0	19	0
Dehydration	11	0	6	2	2	0
Vascular disorders						
Hemorrhage ^d	16	5	11	0	8	2
Renal and urinary disorders						
Renal failure ^e	7	7	2	0	0	0
Hematology						
Leukopenia	62	5	46	4	21	0
Neutropenia	55	13	37	2	9	2
Liver function tests						
Increased AST	60	5	54	0	15	0
Increased alkaline phosphatase	60	2	67	6	26	2
Increased ALT	42	4	35	4	11	0
Hyperbilirubinemia	15	0	7	4	0	0
Chemistry						

Selected AEs and Laboratory Abnormalities Occurring in $\geq 10\%$ at (All Grades) or $\geq 5\%$ (Grades 3 or 4) of Patients Treated With Dabrafenib in Combination With Trametinib

Adverse Reaction or Laboratory Abnormality	Dabrafenib + Trametinib 2mg (n=55)		Dabrafenib + Trametinib 1mg (n=54)		Dabrafenib (n=53)	
	All Grades ^a	Grades 3 and 4	All Grades ^a	Grades 3 and 4	All Grades ^a	Grades 3 and 4
Hyperglycemia	58	5	67	6	49	2
Hyponatremia	55	11	48	15	36	2
Hypophosphatemia	47	5	41	11	40	0

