6. DOSING DELAYS/DOSE MODIFICATIONS

The criteria for dose modification of dabrafenib, trametinib, and INCB039110 are detailed below. In the setting of toxicities of sufficient severity justifying dose modification, every effort will be made to identify the related medication. In the setting where the offending agent is difficult to determine, dose modification will occur with each agent according to the specified dose modifications for each agent.

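### Section 6.2.1 treats severe blood-count effects of dabrafenib plus trametinib as rare, yet the protocol's own table shows 13% Grade 3-4 neutropenia at this dose, and its sections disagree on which drug to modify

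*Combined protocol and SAP*

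**What the plan says.** Section 6.2.1 opens by listing falls in neutrophils, hemoglobin and platelets as the consistent effects of INCB039110. It continues: "For occurrences of grade 3 or 4 events by CTCAE in any of these three categories, the dose reduction table below will be followed". Next comes the premise, "Dabrafenib and trametinib rarely cause severe effects on blood counts", and then the rule drawn from it: "Therefore, in INCB039110 will be modified in the case of severe decreases in blood counts, assuming that these events are considered treatment related". The sentence is garbled, but its opening word ties the rule to the premise.

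Other parts of the protocol bear on the same event:

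- **Section 2.3.2.4**, combination safety table, column headed "Dabrafenib + Trametinib 2mg (n=55": the rows read "Neutropenia 55 13 37 2 9 2" and "Leukopenia 62 5 46 4 21 0". The figures are percentages, all grades then Grades 3-4, for the 150/2 arm, the 150/1 arm and dabrafenib alone.
- **Section 2.3.1**, earlier report of the combination: Grade 3 neutropenia in two patients, 4%.
- **Section 5.1.2**: from Cycle 2, the Day 1 criteria for neutrophils, white cells, hemoglobin and platelets all refer to the table in Section 6.2.1.1, which is the INCB039110 table (Table 6-15).
- **Section 6**, opening paragraph: every effort is to be made to find the responsible drug. Failing that, "In the setting where the offending agent is difficult to determine, dose modification will occur with each agent".
- **Section 6.1.1**, Table 6-1: a default for the doublet, covering treatment-related toxicities that have no section of their own.

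**The concern.** The reason given for singling out INCB039110 is a statement about the doublet that the protocol's own table does not support for neutrophils. The condition that the event be treatment related does not separate the cases: doublet neutropenia is treatment related too, and Section 6.2.1 does not ask which agent caused it.

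Three things are at stake. First, an investigator facing Grade 3-4 neutropenia can reach different actions depending on which section is opened first. Second, INCB039110 exposure may be lowered for an event it did not cause. Section 13.3.1 plans to take reductions of any or all study drugs into account when exploring efficacy. Third, Section 1.2 makes cohort-level dose changes depend on which drug is judged responsible, so a presumption about attribution reaches into dose finding.

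**Working it through.** **1. Does the table match this trial's doublet?** Table 5.1 gives dabrafenib 150 mg BID with trametinib 2 mg QD at levels -1, 1, 2 and 3. Only level -2 differs. The 150/2 column is therefore the relevant one.

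**2. The 13% as a count.** The only whole number out of 55 that rounds to 13% is 7: 7/55 = 12.7%. The exact (Clopper-Pearson) 95% limits are the 0.025 quantile of Beta(7, 49) and the 0.975 quantile of Beta(8, 48), giving 5.3% to 24.5%. The point estimate is about 1 in 8 and the lower limit about 1 in 19. Neutropenia has the highest Grade 3-4 rate in that column; hyponatremia is next at 11%. Grade 3-4 leukopenia is 5% (3/55 = 5.5%).

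**3. Lower figures in the same document.** The 150/1 arm shows 2% (1/54 = 1.9%), as does dabrafenib alone (1/53 = 1.9%). The earlier report in Section 2.3.1 gives 4% at Grade 3 over mixed dose levels. It says the only Grade 4 event was a sepsis-like syndrome, so 4% also serves there as the Grade 3-4 figure.

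**4. How often would the conflict arise?** Section 13.1 tabulates the chance of at least one event among 20 patients. The formula is 1 - (1 - p)^20. It reproduces the plan's rows: p = 0.10 gives 0.878 (plan 0.88) and p = 0.15 gives 0.961 (plan 0.96). Applied to doublet neutropenia, assuming the earlier rate carries over and INCB039110 adds nothing:

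| Assumed rate | Expected in 20 | P(at least 1 of 20) | P(at least 1 of 6) |
|---|---|---|---|
| 13% | 20 × 0.13 = 2.6 | 1 - 0.87^20 = 0.94 | 1 - 0.87^6 = 0.57 |
| 4% | 20 × 0.04 = 0.8 | 1 - 0.96^20 = 0.56 | 1 - 0.96^6 = 0.22 |
| 5.3% (lower limit) | 1.1 | 0.66 | 0.28 |
| 24.5% (upper limit) | 4.9 | 0.996 | 0.82 |

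These are chances that a patient falls under the conflicting rules. They are not rates of wrongly directed reductions.

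**5. The instructions for one patient with treatment-related Grade 3 neutropenia.**

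| Place | What it directs |
|---|---|
| Section 5.1.2 (Cycle 2 onward) | Go to the INCB039110 table; no attribution step |
| Section 6.2.1 | Modify INCB039110; silent on the doublet |
| Section 6, opening | Identify the drug; if that is difficult, modify each agent |
| Table 6-1 | Appears to apply to the doublet by default, since Section 6.1 has no blood-count table: interrupt, restart one level lower |
| Table 6-15 | Titled for INCB039110, but its actions refer to study treatment without saying which drugs |

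The two tables also differ at Grade 4. Table 6-1 offers permanent discontinuation or interruption at first occurrence; Table 6-15 directs interruption, with discontinuation on recurrence.

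**The case against.** The best defence is that Section 6.2.1 does not rest on the word rarely alone. It names neutrophil decreases as an INCB039110 effect, and the Section 6 attribution rule stands over everything below it, so an event clearly due to the doublet can be handled under Section 6.1. Both points are fair. They rule out saying that the protocol would necessarily cut INCB039110 for doublet toxicity; the text supports only that it may. They do not make 13% rare, and the Section 6 fallback of modifying every agent is itself a different instruction from Section 6.2.1.

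Three stronger readings are tempting and should be resisted:

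- **That the doublet continues unchanged.** Section 6.2.1 does not say that only INCB039110 is modified. Table 6-1 appears to cover the doublet, and Table 6-15 may do so through its wording. The supportable finding is ambiguity.
- **That INCB039110 hardly causes neutropenia, at most 4 of 87 (4.6%) at any grade.** The table in Section 2.2.4, headed "Treatment-Emergent Adverse Events Occurring in ≥ 5 Subjects in Study INCB 39110-230", has no neutropenia row. It is organised by preferred term, so the bound holds for that one term only. The same table lists blood bilirubin increased and hyperbilirubinemia as separate rows. The patients had myelofibrosis, and the doublet table includes laboratory abnormalities, so the two are not shown to count the same thing.
- **That the premise fails for all blood counts.** The doublet table has no hemoglobin or platelet rows, while anemia (39.1%) and thrombocytopenia (25.3%) are prominent for INCB039110. The conflict is shown for neutrophils, with leukopenia at 5% alongside.

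Nor does it follow that the adverse-event record would misattribute the toxicity. Section 7.1 grades attribution separately, and Section 13.3.2 summarises events by relationship to treatment.

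**Conclusion.** The point holds in a limited form. For neutrophils, the premise in Section 6.2.1 is contradicted by the protocol's own 13% at the doublet dose used at levels -1 to 3, and the sections governing the response to such an event do not agree. INCB039110 may be reduced for neutropenia that the doublet may have caused, and the handling of the doublet is left unclear.

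On size, a full expansion cohort of 20 is more likely than not to meet the conflict even at the 4% figure, and very likely to at 13%. This assumes that rates from the earlier study apply here. The 13% rests on about seven events, hence the wide interval, and the lower figures come from a different trametinib dose or from mixed doses. The internal contradiction does not depend on that assumption. The matter should be settled because it bears on patient safety and on dose attribution, but it does not undermine the design.

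**What to change.** Two wording changes:

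1. In Section 6.2.1, replace the premise, for neutrophils and leukocytes, with the figures already in Sections 2.3.1 and 2.3.2.4, and repair the garbled sentence that follows it.
2. Reconcile Section 5.1.2, the opening of Section 6, Table 6-1, Section 6.2.1 and Table 6-15, so that a Grade 3-4 fall leads to one instruction stating what applies to each of the three drugs. Table 6-15 should say which drugs its actions cover.

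The clinical team chooses the rule; this review takes no view on it. The cost is a protocol wording amendment, with no additional patients, visits or assessments.
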